### 8.1.1.2. Statistical Analysis

Bayesian analysis for continuous endpoint	
Endpoints	Change from baseline in Complete Mayo Score at Week 10
Statistical analysis	Linear regression
Predictors	
 
● TRT = study treatment(categorical)
 
● Advanced Therapy Experience (categorical) (includes interaction with study treatment)
 
● Baseline Complete Mayo (continuous)
 
● Duration of disease, years (continuous)
 

Model	$y_i \sim \text{Normal}(\text{mean}=\mu, \text{SD}=\sigma)$ $\mu = (\text{TRT=Placebo}) \times (\text{Experienced}=Y) \times \beta_1 +$ $(\text{TRT}=450\text{mg}) \times (\text{Experienced}=Y) \times \beta_2 +$ $(\text{TRT=Placebo}) \times (\text{Naive}=Y) \times \beta_3 + (\text{TRT}=450\text{mg}) \times (\text{Naive}=Y) \times \beta_4$ $+ (\text{Duration}^*) \times \beta_5 + (\text{Baseline}^*) \times \beta_6$

Bayesian analysis for continuous endpoint	
Population-level coefficients ( $\beta$ )	
 
• <math>\beta</math> = fixed effects, parameters associated to predictors  <math>\beta_k</math>: non-informative prior distributions,  <math>\beta_k \sim \text{Normal}(\text{mean}=0, \text{SD}=100)</math>
 
• Standard deviation <math>\sigma</math>:  Non-informative prior Gamma distribution (shape=2, rate=0.1) (Chung, 2013)
 

\* Unless otherwise specified the predictors (not including study treatment) will be centred around their estimated mean in the model

Further details of primary analysis	
Model diagnostics and checking	
	
 
• Each chain will initially have length Of 1,000,000, thin of 10 and burn-in length of 50,000.
 
• Chain convergence diagnostics will be saved in HARP (refdata folder) and inspected.
 
• The MCSE will be compared with the standard deviation of the posterior distribution (SD) to ensure that only a fraction of the posterior variability is due to simulation error, i.e., the ratio MCSE/SD should be close to 0.01
 

Model results presentation	
	
 
• The posterior distribution of each arm and the treatment difference (overall and by Advanced Therapy Experience) will be summarized using median and equal-tailed 95% credible region and the probability of being above specific thresholds specified in the programming notes for this output.
 
• Posterior density plots will be available in model output but will not be presented
 

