9.2.2. Sample Size Re-estimation

At interim analyses 2, 3 and 4 (see Section 9.5) the sample size may be re-estimated based on emerging data. This will be based on the change from baseline in the continuous Mayo score. The sample size may need to be re-estimated if higher variability or differing placebo means are observed compared to those the study has been designed on. Therefore, any significant deviation from the assumptions used to power the study may result in changes to the study population including the number of participants to be randomized.

As part of this re-estimation if the distribution of the advanced therapy experience status (naïve or experienced) is unbalanced across the treatment groups then the recruitment strategy may be altered to establish a balance. A maximum of 320 participants could be randomized into the study following this sample size re-estimation.

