	
 • If the four parameter Emax model is not applicable then additional models will be investigated: three parameter Emax model, power model, linear, quadratic, log-transformed dose. Each of the models will be fitted to the data and their fit compared using the Deviance Information Criterion (DIC), where the model with the lowest DIC will be the primary model for inference. • Prior medication will be included as a stratification factor: advanced therapy naïve, experienced a single class of advanced therapy, or experienced multiple classes of advanced therapies. • Further details of the Emax model will be defined in the RAP. • The primary analysis will use the ITTE analysis population. • The primary estimand will use a treatment policy strategy for intercurrent events, with the exception of discontinuations due to COVID-19 pandemic which will use a hypothetical strategy. • Under the hypothetical strategy, data set to missing would be assumed to be missing at random (MAR).
Secondary	
 • Analyses of the secondary endpoints will be conducted using similar methodology as for the primary endpoint (with an appropriate link-function for binary endpoints). • The decision criteria at the interim analyses 3 and following completion of the primary analysis will primarily be based on the proportion of participants who achieve endoscopic healing. These are based on predictive probabilities based on the data available. Details are outlined in Section 9.5, and in the interim analysis charter and RAP.
Exploratory	
 • Will be described in the RAP.

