## 5.4. Examination of Covariates, Other Strata and Subgroups

### 5.4.1. Covariates and Other Strata

The following list of covariates and other strata will be used in descriptive summaries and statistical analyses of primary and key secondary efficacy endpoints, some of which will also be used for subgroup analyses. Additional covariates and other strata of clinical interest may also be considered. For change from baseline endpoints, the baseline will also be included as a covariate.

Category	Details	Notes
Advanced therapy experience (Stratification factor)	Categorical variable with three levels: 
 
Advanced therapy naïve,
 
Single class of advanced therapy experience
 
Multiple classes of advanced therapy experience
 
	Derived from 'previous UC medications' in medical history.  This is the stratification factor used in RAMOS, recorded at baseline in the eCRF for each participant; in case of conflict between the stratification in RAMOS and medical history, medical history will be used.
TNF failure (Covariate)	Categorical variable with three levels: 
 
No TNF failure
 
Single TNF failure
 
Multiple TNF failures
 
	Derived from medical history, covariate will be used as secondary analysis at primary completion
biologic experience type (Covariate)	Categorical variable with three levels: 
 
Biologic naïve
 
TNF experience (no Vedolizumab)
 
Vedolizumab (including participants who have both TNF and Vedolizumab experience)
 
 
Note: if participant has experience of other biologics, they will be assigned based on experience of TNF and Vedolizumab.
	Derived from medical history. Comparison made as secondary analysis.
Baseline mucosal CD3+LAG3+ cell count (Covariate)	Continuous variable derived from biopsy.  CD3 positive and Lag3 positive cells per mm  of Lamina Propria tissue taken at screening biopsy.	
Duration of disease (Covariate)	Duration of disease, years	If day and month of diagnosis are missing, duration of disease will be calculated by using day=1 and month=July
Baseline Complete Mayo Score	Where the endpoint is derived from a version of the Mayo score, that version's baseline will be used.	

Category	Details	Notes
Baseline Adapted Mayo Score	Where the endpoint is derived from a version of the Mayo score, that version's baseline will be used.	

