#### 5.4.2. Examination of Subgroups

The list of subgroups may be used in descriptive summaries and statistical analyses. Additional subgroups of clinical interest may also be considered. The following subgroup analyses will only be performed at final analysis unless otherwise specified.

- If the percentage of subjects is small within a particular subgroup, then the subgroup categories may be refined prior to unblinding the trial.
- If the category cannot be refined further, then descriptive rather than statistical comparisons may be performed for the particular subgroup.

Subgroup	Categories	Timing	Motivation
Any advanced therapy experience	Advanced therapy naïve vs. Advanced therapy experienced	Interims, SAC	Prior expectation of clinical importance

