### Informative Placebo Prior

- The prior distribution is a robust mixture prior based on historical data following the approach of ([Schmidli, 2014](#)). A meta analytic predictive (MAP) prior of relevant historical data is created, with a covariate for the proportion of Advanced Therapy Experienced in each historical trial.
- The MAP prior is obtained via an MCMC model with the following specifications:
  - For each historical trial  $s$  with  $r$  responders in  $N$  placebo patients and percentage of Advanced Therapy Experienced  $\%Exp$ :
 
$$r_s \sim \text{Binomial}(\text{size} = N_s, \text{rate} = \text{rate}_s)$$

$$\text{rate}_s = \text{logit}^{-1}(\alpha + \beta * \%Exp_s + \epsilon_s)$$

$$\epsilon_s \sim \text{Normal}(0, \tau)$$
  - Prior for between-trial heterogeneity  $\tau$ : half-normal with  $\mu=0$ ,  $\sigma=z/2$  where  $z$  is derived via the  $n\infty$  method ([Neuenschwander., 2010](#)):
    - $p$  = mean of  $r/N$  of historical trials
    - $z = [\sqrt{p^*(1-p)}]^{-1}$
  - Priors for coefficients  $\alpha, \beta$ : normal with  $\mu=0$ ,  $\sigma=100$
- The MCMC samples of the placebo response are approximated using appropriate parametric distributions, typically a mixture of two to three Beta distributions. Unless stated otherwise, the number of Beta distributions in the mixture is decided via AIC.
- The prior used for analysis will use the proportion of Advanced Therapy Experienced participants observed in this trial at the relevant interim or final analysis.
- The rules for including historical data used for this analysis will be documented in [Appendix 14: Details of the Informative Placebo Prior](#).
- The MAP prior distribution is 'robustified' by further mixing with a non-informative Beta(1/2,1/2) distribution with 40% weight for the non-informative prior.
- The final prior distribution and supporting information will be documented in the trial master file before the study is unblinded for interim analysis 3.
- Examples of the parametric distributions used at different levels of the covariate are documented in [Appendix 14: Details of the Informative Placebo Prior](#).

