#### 8.2.3.1. Statistical Analysis

Bayesian Repeated Measures Analysis for Continuous Endpoint	
Endpoint	Change from baseline in Partial Mayo Score
Statistical analysis	GLMM with natural link (equivalent to MMRM)
Model	$\mathbf{y}_i \sim \text{Normal}(\boldsymbol{\mu}_i, \sigma^2 \mathbf{I}_J)$ $\boldsymbol{\mu}_i = \mathbf{X}_i \boldsymbol{\beta} + \mathbf{Z}_i \mathbf{b}_i$
Outcome	$\mathbf{y}_i$ = vector of change from baseline values for participant $i$
Prior for $\sigma$	$\sigma$ = between-participant SD, $\sim \text{Gamma}\left(2, \frac{1}{A}\right)$ with A reasonably large e.g. A=10 (Chung, 2013)
Population-level coefficients ( $\boldsymbol{\beta}$ )	
 
<math>\boldsymbol{\beta}</math> = fixed effects, parameters associated to predictors  <math>\beta_0</math> = intercept, two possible prior distributions*:  Vague: <math>\text{Normal}(0, sd = 100)</math>  Weakly informative: see Appendix 14: Details of the Informative Placebo Prior  <math>\beta_k \sim \text{Normal}(0, sd = 100)</math>
 

Bayesian Repeated Measures Analysis for Continuous Endpoint	
Predictors ( X )	
 
• TRT = study treatment(categorical)
 
• visit = visit (categorical)
 
• TRT*visit = study treatment by-visit interactions (categorical)
 
• BASE = baseline value of dependent variable (continuous) 
 
• Partial Mayo Score
 
 
 
• BASE*visit =baseline value by-visit interactions (continuous)
 
• Advanced therapy experience (categorical stratification variable)
 

Random effects ( b )	
 
• <math>Z_i</math> = known design matrix for the random effects
 
• <math>b_i</math> = unknown subject-level random effects, <math>\sim \text{Normal}(0, \Sigma_b)</math>, where <math>\Sigma_b</math> within-subject covariance matrix
 
• <math>\Sigma_b \sim \text{Inverse Wishart}(J, S)</math>, with <math>J</math> = number of visits (degree of freedom), <math>S</math> = covariance matrix (identity matrix)
 

\* The parameterisation of the priors used in the analysis will be reported in the clinical study report.

The details of the scores and indexes including the Complete, Partial and Adapted Mayo scores, and the corresponding definition of response and remission are described in Section 15.6 Appendix 6: Derived and Transformed Data.

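### The primary model merges two of the three prior-therapy strata without listing the change, and it has no term for the 450 mg:placebo allocation ratio in force (low severity)

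*SAP*

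**What the plan says.** **Prior therapy.** For the primary efficacy analysis, Protocol 9.4.1 states: "Prior medication will be included as a stratification factor". It then gives three levels: naive, one class of advanced therapy, more than one class. SAP 5.4.1 defines the same three-level variable, the third level being "Multiple classes of advanced therapy experience". It identifies the variable as the factor used at randomisation and says its covariate list "will be used in descriptive summaries and statistical analyses of primary and key secondary efficacy endpoints".

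The models do not match this:
- **Primary (SAP 8.1.1.2):** the predictor is "Advanced Therapy Experience (categorical) (includes interaction with study treatment". The equation has four cells, placebo or 450 mg crossed with experienced or naive.
- **Key secondary (SAP 8.2.1.2):** the factor is called categorical but has a single coefficient. SAP 8.2.2 reuses this model for clinical remission.
- **Partial Mayo (SAP 8.2.3.1):** the predictor is "Advanced therapy experience (categorical stratification variable", which under SAP 5.4.1 has three levels.

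For the primary model, SAP 2.1.4 lists only the restriction to the 450 mg and placebo arms.

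**Allocation.** Protocol 4.1 and SAP 2.3 randomise 450 mg to placebo at 2:1, then open all arms at 2:3:3:3:2, which is 1:1 for these two arms. Protocol 6.4.1 lets 2:1 continue among Japanese participants after the switch. The primary model has no term for the ratio in force.

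**The concern.** The factor that the trial stratified by, and that the protocol names for the primary analysis, enters the primary model in a coarser form. A reader who relies on the SAP's list of changes would not learn this. The primary and Partial Mayo analyses are reported at the same final analysis (Tables 2.12 and 2.14), so two results shown together may adjust for different versions of one factor. The primary equation also cannot give separate single-class and multiple-class estimates, although SAP 8.1.1.2 promises treatment differences by advanced therapy experience without saying how many levels are meant.

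The allocation point is different in kind. When the ratio changes during recruitment, the two arms hold different shares of early and late participants. If outcomes differ between the stages for reasons that baseline score, disease duration and experience do not capture, part of that difference enters the 450 mg versus placebo contrast.

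**Working it through.** **1. Reproduce the planned arm sizes.** Protocol 9.2.1 gives 40 and 20 participants for Interim Analysis 3 and 242 in total. Stage 2 is then 242 − 60 = 182 over 2+3+3+3+2 = 13 ratio units, or 14 per unit: 28, 42, 42, 42 and 28. The final sizes are 40 + 28 = 68 on 450 mg, 42 on each lower dose and 20 + 28 = 48 on placebo. These match the protocol.

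**2. Stage bias.** Let n be the number of stage-2 participants per arm with an analysable Week 10 value, and d the stage difference in Mayo points left after the modelled covariates. Neither is in the documents; both are assumed. The size of the bias is d × [40/(40+n) − 20/(20+n)]. With SD 1.5 (Protocol 9.2.1), the unadjusted SE is 1.5 × √[1/(40+n) + 1/(20+n)]. The stage-adjusted SE is 1.5/√(800/60 + n/2).

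| n per arm | Bias | SE without stage term | SE with stage term | Bias/SE at d = 0.5 |
|---|---|---|---|---|
| 0 | 0 | 0.411 | not needed | 0 |
| 2 | 0.043d | 0.395 | 0.396 (+0.4%) | 0.05 |
| 4 | 0.076d | 0.381 | 0.383 (+0.6%) | 0.10 |
| 10 | 0.133d | 0.346 | 0.350 (+1.1%) | 0.19 |
| 28 (planned) | 0.172d | 0.283 | 0.287 (+1.5%) | 0.30 |

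For n up to 10, the bias is at most 0.07 points at d = 0.5 and 0.13 points at d = 1. The latter is 0.13/2 = 7% of the 2-point difference used in Protocol 9.2.1.

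**3. Which n is plausible.** SAP 2.4 refers to low numbers on the three middle doses. In stage 2, 450 mg and placebo each receive two thirds of a middle dose's allocation. SAP 8.1.1.1 also sets assessments after sponsor-termination discontinuations to missing, even when collected. Both point to a small n; neither gives it.

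**4. Cost of merging two classes.** Assume two thirds of participants are experienced, a share p of those have multiple classes, and single- and multiple-class means differ by g points. The SE ratio is √[1 + (2/3) × p(1−p) × g²/1.5²].
- g = 0.5, p = 0.3: √1.0156, or +0.8%.
- g = 1, p = 0.5: √1.0741, or +3.6%.

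With 80% experienced, p = 0.5 and g = 1, it is √[1 + 0.8 × 0.25/2.25], or +4.3%. Hence about 1% to 4%. Because treatment was randomised, merging does not shift the expected difference.

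**5. Cost of the added terms.** I simulated designs for the SAP 8.1.1.2 model with its treatment interaction, under the same experience assumptions.
- The class coefficient alone raises the SE of the overall difference by 0.9%, 0.8%, 0.7% and 0.5% at n = 0, 4, 10 and 28.
- Class and stage together raise it by 1.5%, 1.9% and about 2.0% at n = 4, 10 and 28.

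**6. Sparse data in the logistic model.** Take the 20% placebo healing rate of Protocol 9.2.1 for both arms. The chance of no stage-2 responder is 0.8⁴ = 41%, 0.8⁸ = 17% and 0.8²⁰ = 1% at n = 2, 4 and 10. Now assume 10% remission and 68 participants (44 + 24, so n = 4). Two thirds experienced, with 30% to 50% of those multiple-class, gives 14 to 23 multiple-class participants. The chance of no remitter among them is 0.9¹⁴ = 23% to 0.9²³ = 9%.

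**The case against.** **Two levels may be intended.** Protocol 9.2.2 uses naive or experienced in the sentence beginning "As part of this re-estimation if the distribution of the advanced therapy experience status". The placebo prior in SAP 8.2.1.2 rests on one proportion: "The prior used for analysis will use the proportion of Advanced Therapy Experienced participants observed in this trial". SAP 5.4.2 has a naive versus experienced subgroup. Protocol 9.4.1 was written for the five-arm Emax analysis and leaves detail to the SAP, and the primary equation is printed in full. SAP 5.4.1 also lists covariates that neither model uses, such as TNF failure, so its list alone does not dictate the model. All this stands as a reason why two levels could be defended. It does not remove the mismatch. SAP 5.4.2 names its split "Any advanced therapy experience", whereas the models use the name that SAP 5.4.1 defines with three levels. The protocol names three levels for the primary analysis specifically.

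**No stage term was promised.** This is correct. A reader might infer that its absence departs from the protocol; no section supports that. Nor is leaving out the Japan stratum a departure from Protocol 9.4.1, which names only prior therapy. The switch depends on the number randomised, not on outcomes, so bias needs a real stage difference, which no document shows.

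**A stage term can do harm in the logistic model.** This also stands. With few stage-2 responders the coefficient can separate and, because predictors are centred, shift the arm terms.

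**The frequentist model (SAP 8.1.1.3)** is not affected by the stage point. Its only listed display is Table 2.27 at Interim Analysis 3, where the ratio is essentially constant.

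**Conclusion.** The point holds at low severity. The two-level coding in the primary model is an unlisted departure from the three-level factor in Protocol 9.4.1. For the key secondary model the same coding is inferred from its single coefficient. For the Partial Mayo model the wording implies three levels, so the analyses may differ.

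A reader might infer that merging the classes biases the primary result. It does not in expectation; the loss is about 1% to 4% in SE under assumed class gaps of 0.5 to 1 point, plus agreement with the protocol.

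The missing allocation term is a gap in the analysis. Its bias is 0 to 0.13d for an assumed 0 to 10 analysable stage-2 participants per arm. A reader might instead take the planned-size figure of 0.17d, but termination makes that unlikely. The bias is probably small, and it is zero if no 450 mg or placebo participant randomised at 1:1 has a Week 10 value in the analysis.

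**What to change.** - **SAP 8.1.1.2:** keep the naive/experienced by treatment interaction and add one centred coefficient for multiple versus single class. Add a centred indicator for the 450 mg:placebo ratio in force at randomisation, so that Japanese participants still on 2:1 count as 2:1. Omit the indicator if no 450 mg or placebo participant randomised at 1:1 has a Week 10 value in the analysis.
- **SAP 8.2.1.2, and clinical remission through 8.2.2:** add the class coefficient with a weakly informative prior, for example Normal(0, SD 2.5) on the logit scale. Use the stage term only in a sensitivity analysis.
- **If two levels are kept:** list and justify this in SAP 2.1.4, and align 5.4.1, 8.2.1.2 and 8.2.3.1.

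The cost is SAP wording and two coefficients from data already held. In the linear model both terms together cost about 1.5% to 2% in SE. On precision alone, the class coefficient pays only if the two classes differ by more than about 0.5 point; below that, the gain is agreement with the protocol.

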### 8.1.1.3. Additional analyses for the Primary Endpoint

Frequentist analysis of change from baseline in Complete Mayo score at Week 10	
	
A fixed-effect normal linear model will be used to compare the primary endpoint (change from baseline in Complete Mayo score at Week 10 Double-Blind Induction) between 450mg GSK2831781 IV and Placebo IV.
 
The following variables will be used as covariates: Duration of disease (continuous), Advanced Therapy Experience (Categorical), Baseline Complete Mayo (continuous) and treatment.
 
The estimated difference in change from baseline in Complete Mayo score at Week 10 will be displayed with 95% confidence interval (and associated p-value).

## 8.2. Secondary Efficacy Analyses

### 8.2.1. Key Secondary Endpoint

#### 8.2.1.1. Estimand

Key secondary estimand for decision making: "Composite"	
Objective:	To investigate the effect of repeat doses of GSK2831781 on clinical efficacy including endoscopic mucosal healing during the Double-Blind Induction Phase.
Estimand:	
Description
 
Difference in response rates between active doses of GSK2831781 and Placebo when added to background therapy in patients with moderate to severe, active Ulcerative Colitis.
 
Attributes
 
 
• Treatment: Placebo and active doses of GSK2831781 in addition to background therapy and stable dose of corticosteroid where relevant.
 
• Population: Patients with moderate to severe, active, Ulcerative Colitis as per inclusion/exclusion criteria.
 
• Outcome measure: Endoscopic Mucosal Healing at Week 10 assessment, where success is defined as: 
 
○ Achieving a score on the endoscopic component of the Adapted Mayo score of 0 or 1, and
 
○ Not discontinuing IP due to reasons unrelated to the COVID-19 pandemic or to sponsor's decision to terminate the study, and
 
○ Not taking medications excluded by the protocol or increasing dose of corticosteroid.
 
 
 
• Intercurrent events and strategy: 
 
○ ICE: discontinuation from IP, unrelated to COVID-19 pandemic or to sponsor's decision to terminate the study.
 
○ Strategy: included in outcome via composite strategy (i.e. post-ICE result set to non-response).
 
○ ICE: discontinuation from IP, due to COVID-19 pandemic.
 
○ Strategy: hypothetical, setting response status to missing.
 
○ ICE: discontinuation from IP, due to sponsor's decision to terminate the study.
 
○ Strategy: hypothetical, setting response status to missing.
 
○ ICE: valid endoscopy result not available, due to COVID-19 pandemic
 
 
 

Key secondary estimand for decision making: “Composite”	
	
 
○ Strategy: hypothetical, setting response status to missing.
 
○ ICE: valid endoscopy result not available, for technical reasons
 
○ Strategy: hypothetical, setting response status to missing.
 
○ ICE: prohibited medication taken
 
○ Strategy: included in outcome via composite strategy (i.e. post-ICE result set to non-response).
 
○ ICE: increase in dose of permitted medications
 
○ Strategy: included in outcome via composite strategy (i.e. post-ICE result set to non-response).
 
● Population-level summary: Difference in proportion of participants who achieve response between placebo and relevant active doses
 

Estimation and missing data details for the key secondary estimand for decision making (“Composite”)	
	
Participants who have a missing assessment at Week 10 for reasons unrelated to the COVID-19 pandemic will be counted as non-responders in the analysis.
 
The ICEs that will be dealt with using a hypothetical strategy will have response status set to missing
 
In all cases, the missing response status will be assumed to be MAR in the statistical analysis.
 
The MAR assumption is implicit in the planned Bayesian analysis.

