	
 ○ Not discontinuing IP due to reasons unrelated to the COVID-19 pandemic, and ○ Not taking medications excluded by the protocol or increasing dose of corticosteroid. 
 ● Intercurrent events and strategy: 
 ○ ICE: discontinuation from IP, unrelated to COVID-19 pandemic. 
 ▪ Strategy: included in outcome via composite strategy (setting response status as non-responder). ○ ICE: discontinuation from IP due to COVID-19 pandemic. 
 ▪ Strategy: handled as though discontinuation had not occurred (hypothetical strategy, setting response status to missing with MAR assumption). ○ ICE: valid endoscopy result not available due to COVID-19 pandemic. 
 ▪ Strategy: handled as though missing assessment had not occurred (hypothetical strategy, setting response status to missing with MAR assumption). ○ ICE: valid endoscopy result not available for technical reasons. 
 ▪ Strategy: handled as though missing assessment had not occurred (hypothetical strategy, setting response status to missing with MAR assumption). ● Population-level summary: Difference in proportion of participants who achieve response between placebo and relevant active doses.
--	---

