#### **2.1.4. Changes to Efficacy Estimands and Statistical Analyses**

The “Hypothetical” additional estimand for Complete Mayo Score has been removed to simplify the reporting of efficacy.

The primary estimand (Complete Mayo Score) and key secondary estimand (Endoscopic Improvement) have been modified to account for “discontinuation due to sponsor’s decision to terminate the study” intercurrent event.

New estimands are defined for secondary continuous and categorical efficacy endpoints. The populations and intercurrent event strategies for these estimand are the same as the Primary estimand for Complete Mayo Score (in the case of secondary continuous endpoints) or Key secondary estimand for Endoscopic Improvement (in the case of secondary categorical endpoints).

The primary dose response model for Complete Mayo Score has been modified to only analyse the 450mg IV and Placebo IV arms due to projected lack of patients randomised to other treatment arms following study termination.

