### 15.6.3.5. Intercurrent Events Selection

If more than one intercurrent event occurs for a subject, then the earliest event will be considered for reporting. If two events occur at the same timepoint, then (for the respective Estimand) the event listed first in the list below will be prioritized:

- Secondary Efficacy Estimand:
  - Discontinuation from IP
  - Valid endoscopy result not available
  - Excluded medication

Note that no distinction is made in the above list between COVID-related discontinuations, discontinuations due to sponsor's decision to terminate the study and other discontinuations, as they are mutually exclusive and a participant can only experience one of these three ICEs. For the same reason, a list for the Primary Efficacy Estimand is not needed.

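### SAP 8.2.1.1: one sentence counts as non-response some missing Week 10 results that the same section sets to missing

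*SAP*

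**What the plan says.** SAP Section 8.2.1.1 defines the key secondary estimand in two parts.

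The first part lists the ICEs with their strategies. Two that do not concern COVID-19 have a hypothetical strategy, with response status set to missing: "discontinuation from IP, due to sponsor's decision to terminate the study", and "valid endoscopy result not available, for technical reasons".

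The second part is a box on estimation and missing data. Its first sentence reads: "Participants who have a missing assessment at Week 10 for reasons unrelated to the COVID-19 pandemic will be counted as non-responders in the analysis". Its second reads: "The ICEs that will be dealt with using a hypothetical strategy will have response status set to missing". The box then says that missing response status is assumed missing at random.

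Three other places bear on the intent:

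- SAP Section 2.1.4: "The primary estimand (Complete Mayo Score) and key secondary estimand (Endoscopic Improvement) have been modified to account for" discontinuation caused by the sponsor's termination.
- SAP Section 8.1.1.1: the corresponding box for the primary estimand names termination beside COVID-19 and sets later assessments to missing.
- Protocol Section 3: an endoscopy lost for technical reasons was already to be "handled as though missing assessment had not occurred (hypothetical strategy, setting response status to missing with MAR assumption".

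**The concern.** The first sentence of the box has its own exception, and that exception covers COVID-19 only. Termination by the sponsor and technical failure of an endoscopy are both reasons other than COVID-19. A participant with either event and no Week 10 result is missing under the ICE list and non-response under this sentence.

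The coding feeds three outputs planned for the final analysis: Table 2.21 (statistical analysis of the categorical endpoints), Table 2.28 (summary after estimand handling) and Figure 2.9 (forest plot after estimand handling). A programmer who follows the sentence as written would code the key secondary endpoint against its own estimand. Listing 69, which shows the estimand imputations, is marked for the Interim Analysis 3 headline only. In the final report a miscoding would have to be inferred by comparing Table 2.17 (observed) with Table 2.28 and Listing 68 (intercurrent events).

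**Working it through.** **Step 1: compare the rules case by case.** In each row the participant has no Week 10 endoscopy result.

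| Case | ICE list and second sentence of the box | First sentence of the box |
|---|---|---|
| COVID-19 discontinuation or missed endoscopy | missing | exempt |
| Stopped because the sponsor ended the study; result absent for a non-COVID reason | missing | non-response |
| No valid result for technical reasons | missing | non-response, if this counts as a missing assessment |
| Stopped for any other reason | non-response | non-response |
| No listed ICE, non-COVID reason | no rule | non-response |

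Rows 2 and 3 conflict. If a Week 10 result exists after a termination discontinuation, only the ICE rule applies and there is no conflict.

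**Step 2: look for a rule of precedence.** SAP Section 15.6.3.5 says: "If more than one intercurrent event occurs for a subject, then the earliest event will be considered for reporting". That orders ICEs against each other. It does not order an ICE rule against the missing-assessment sentence. The missing-at-random sentence says how missing values are treated, not which cases are missing. No precedence is stated.

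**Step 3: can row 2 occur?** The schedule of activities (footnote 22) asks for an endoscopy at early withdrawal only if treatment stops after Week 4. SAP Section 15.3.1 places early-withdrawal visits by actual date, and its Week 10 window opens on Day 58. A participant stopped by the termination whose last endoscopy came before Day 58 has no Week 10 value.

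**Step 4: effect on a crude response rate.** The plan states no figure to reproduce here. Let an arm have r responders among n participants with a result, and m affected participants.

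- Coded missing: p = r/n.
- Coded non-response: r/(n+m) = p(1 − s), where s = m/(n+m).
- Difference under literal coding: p1(1 − s1) − p0(1 − s0), a shift of p0·s0 − p1·s1.

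Inputs: p0 = 20% is the placebo response in Protocol Section 9.2.1. p1 = 40% and all affected shares are assumptions.

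| Affected, active / placebo | Active | Placebo | Difference (points) |
|---|---|---|---|
| 0% / 0% | 40% | 20% | 20 |
| 5% / 5% | 38% | 19% | 19 |
| 10% / 10% | 0.40 × 0.90 = 36% | 0.20 × 0.90 = 18% | 18 |
| 20% / 20% | 32% | 16% | 16 |
| 30% / 30% | 28% | 14% | 14 |
| 20% / 10% | 32% | 18% | 14 |
| 10% / 20% | 36% | 16% | 20 |

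With no true effect (20% in both arms), equal shares give a difference of 0. Shares of 20% / 10% give 16% − 18% = −2 points, and 10% / 20% give +2 points.

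These figures are for crude proportions, so they bear on Table 2.28 and Figure 2.9 only.

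**The case against.** The strongest reply is that the intended coding can be recovered. The success definition, the ICE list, the change log in Section 2.1.4 and the second sentence of the box all point to missing for termination. The first sentence can be read as a default for missing data that no ICE explains, with the second sentence as the specific rule. That is probably what was meant. It does not remove the conflict, because the first sentence carries its own exception and that exception is incomplete.

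Four further objections stand and limit the point:

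- **Technical failures.** A reader might put both conflicts down to a missed update after termination. The documents do not support that, because the protocol already gave the technical-failure ICE a hypothetical strategy. This limb is also less clear: an endoscopy may have been done but be unreadable, which is not plainly a missing assessment.
- **Reason for the missing result.** A reader might use Section 15.6.3.5 to show that a termination case cannot be a COVID-19 case. The section calls the three kinds of discontinuation separate, "as they are mutually exclusive and a participant can only experience one of these three ICEs". It does not classify why an endoscopy is missing. Someone who stopped because of termination could still have missed the endoscopy because of COVID-19.
- **Model estimate.** The shifts above do not carry over to Table 2.21. That estimate comes from a covariate-adjusted Bayesian logistic model with an informative placebo prior (Section 8.2.1.2).
- **Consequence.** The study was stopped before Interim Analysis 4 and primary completion, so what remains is final reporting. One sponsor decision also applied to both arms, so very unequal shares are a less natural assumption.

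**Conclusion.** The point holds as an internal contradiction in SAP Section 8.2.1.1. A stated rule, followed literally, miscodes the key secondary endpoint against its estimand. The termination limb is clear, and the technical-failure limb is plausible but weaker.

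The size is unknown, because the documents give no count of affected participants. For crude rates, under the protocol's 20% on placebo and an assumed 40% on active, a 20-point difference falls to 18 if 10% are affected in both arms, and to between 19 and 14 for equal shares of 5% to 30%. The shift in the Bayesian estimate is not computed.

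A reader might infer that the final results are wrong. The documents do not show this: if the hypothetical coding was programmed, the sentence adds no bias, although the analysis still relies on missing at random. A reader might also be sure that the sentence is leftover text. That is likely for termination, but earlier versions of the SAP would be needed to confirm it. Finally, the contradiction should not be extended to the categorical endpoints of Section 8.2.2. That section takes over the ICE strategy, not this box, and a missing-data rule for those endpoints, including diary-based symptomatic remission, is a separate choice.

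**What to change.** Reword the first sentence of the box along these lines:

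> A participant whose Week 10 assessment is missing counts as a non-responder unless the missing result is covered by an ICE with a hypothetical strategy (COVID-19, termination of the study by the sponsor, or technical failure of the endoscopy), as selected under Section 15.6.3.5.

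Name both non-COVID events, since adding termination alone would leave the technical-failure conflict in place. Do not simply declare that hypothetical-strategy ICEs always prevail. Under Section 15.6.3.5 the earliest event counts, so an earlier composite ICE, such as use of a prohibited medication, must still give non-response.

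Then check the response flag in the analysis dataset against the reworded rule.

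The cost is one sentence in the SAP and a check of one derived variable. No new data are needed.
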